Static load to failure testing our laboratory has challenged this observation in vertical medial malleolus fracture patterns as well.⁵⁻⁷ We recently demonstrated (manuscript submitted) superior stiffness (463 ± 91 N/mm) and load at 2 mm of ankle joint displacement (922 ± 297 N) with antiglide plate fixation versus unicortical screw fixation (111 ± 35 N/mm and 284 ± 51 N, respectively) and bicortical screw fixation (279 ± 30 N/mm and 429 ± 112 N, respectively) of vertical medial malleolus fractures ($p < 0.05$).

Superior fixation requires extensive dissection and fixation known to result in prominent hardware and hardware related pain. None of these fixation methods address the lack of soft tissue to cover the medial malleolus and the common practice of hardware removal to address post-fixation hardware pain. Retrospective review of ankle hardware removal cases indicates that 6% (8/126) of patients have their hardware removed for non-pain issues (e.g., infection, etc.) at 6 months and 17% (22/126) of patients have their hardware removed for pain on the medial or lateral side of the ankle at 6 months.⁸

The headless configuration of the Acutrak system makes it ideal for medial malleolus fixation and may obviate the need for hardware removal. We recently demonstrated (manuscript submitted) superior stiffness and load at 2 mm of ankle joint displacement of an Acutrak screw construct (244 ± 58 N/mm and 483 ± 91 N, respectively) when compared to partially threaded parallel unicortical cancellous screw construct (111 ± 35 N/mm and 278 ± 49 N, respectively) in static load

[figure not shown]

Figure 1: Vertical shear medial malleolus fractures fixed with cancellous screws (left) and Acutrak screws (right) demonstrating the lack of hardware prominence after fixation as well as maintenance of reduction after off-set axial loading.

to failure testing of vertical medial malleolus fractures. Additionally, when the specimens were displaced to 6 mm and allowed to relax, the Acutrak headless compression screw constructs reduced to the pretesting fragment alignment while the parallel cancellous constructs remained displaced (see Figure 1).

HYPOTHESIS

The fixation provided by the Acutrak headless compression screws provide sufficient fixation to achieve union and a favorable clinical outcome in both horizontal and vertical medial malleolus fractures when compared to bicortical and unicortical screw fixation, tension band wiring, and mini-fragment or buttress plating. However, minimizing the amount of dissection required for implantation as well as lack of prominent hardware surfaces will reduce the incidence and severity of hardware related pain and correspondingly the necessity of hardware removal.

Specific Aims

- 1) *Prospectively establish equivalence with respect to fracture union rate after Acutrak headless compression screw fixation when compared to other fixation methods for medial malleolus fractures.*
- 2) *Prospectively establish equivalence with respect Patient Reported Outcome Measurement Information System (PROMIS) scores after Acutrak headless compression screw fixation when compared to other fixation methods for medial malleolus fractures.*
- 3) *Prospectively establish superiority with respect to hardware related pain after Acutrak headless compression screw fixation when compared to other fixation methods for medial malleolus fractures.*
- 4) *Prospectively establish superiority with respect to the hardware removal rate after Acutrak headless compression screw fixation when compared to other fixation methods for medial malleolus fractures.*

Study Design

Institutional Review Board and HIPAA

The institutional review boards of Stanford Hospital and Clinics and the Kaiser Permanente Hospital, South Sacramento will review and approve this study prior to initiation. All patient information will be kept confidential in accordance with HIPAA and only the study coordinator and the protocol director will have access to the data.

Inclusion/Exclusion Criteria

All ankle fractures that undergo open reduction internal fixation of the medial malleolus in adults at or over 18 years-of-age will be considered for inclusion.

We will specifically exclude pediatric ankle fractures in children under 18 years-of-age, tibial plafond (pilon) fractures in children and adults, medial malleolar osteotomies to access the talus, perform an ankle fusion, or deal with a pathologic lesion, osteonecrosis, or infection due to their diversity in diagnosis, management, and weight bearing status. Patients with prior surgical treatment of the ankle for fracture, deformity, infection, neoplasia, or other pathologic process on the ipsilateral extremity will also be excluded.

Patients that are non-weight bearing on one or both lower extremities prior to sustaining their ankle injury will be excluded.

Randomization

All elective and emergent admissions to Stanford Hospital and Clinics and Kaiser Permanente – South Sacramento that meet our inclusion/exclusion criteria will be identified and solicited for consent. Patients will be randomized by sealed envelope to surgical fixation with traditional headed screws, plates, and wires or Acutrak headless compression screws. At the time of randomization, the fracture pattern and severity, past medical history and medications, and demographic data will be documented.

Follow-up Protocol

After operative fixation, patients will receive fracture follow-up with a clinical evaluation for tenderness, radiographs to evaluate stability and union at 2 weeks, 6 weeks, 3 months of surgery and complete the PROMIS and VAS pain scores. Patients will be followed by telephonically once the fracture union is confirmed radiologically by the operating surgeon at 6 months, 1 year, and 2 years after surgical fixation. The VAS pain scores will be administered telephonically and the PROMIS questionnaires will be mailed to the patients (Table 1).⁹

Table 1: Protocol Summary

Time and Event Table	Injury/Office	2 weeks	6 weeks	3 months	6 months (over Telephone & mail)	1 year (over Telephone & mail)	2 years (over Telephone & mail)
Discuss Study	X						
Screening Log	X						
Informed Consent	X						
Eligibility Worksheet	X						
Demographic Data	X						
Medical History	X						
Randomization	X						
Clinical Assessment							
•Medial Ankle Tenderness	X	X	X	X	X	X	X
•Lateral Ankle Tenderness	X	X	X	X	X	X	X
Patient Reported Outcomes							
•PROMIS Score	X	X	X	X	X	X	X
•VAS Pain (by location)	X	X	X	X	X	X	X
•On Narcotics (yes/no)	X	X	X	X	X	X	X
Radiographs							
•Anterior-to-Posterior Ankle	X	X	X	X	-	-	-
•Lateral Ankle	X	X	X	X	-	-	-
Operative/Device	X						
Removal of Hardware		X	X	X	X	X	X
Adverse Event	X	X	X	X	X	X	X
End of Study							X

Criteria for Removal of Hardware

Hardware may be removed if there is a surgical indication or patient/surgeon preference for removal. Patients will be asked whether they feel bothersome sensitivity at the both medial and lateral malleolus. If they mention sensitivity to light touch that is not bothersome they should not be subjected to hardware removal unless by patient or surgeon preference and noted as medial or lateral hardware removed for preference. On the other hand, if they mention bothersome sensitivity, it would be rated on a 0-5 Likert intensity scale. All bothersome sensation will be subjected to hardware removal and noted as removal for sensitivity. Other reasons for hardware removal indications include infection and non-union or mal-union requiring revision open reduction and internal fixation. The location of symptoms and reason for hardware removal should be specified and documented.

Documentation of Fracture Union

Union will be defined as a pain free fracture site on examination with evidence of radiographic healing and a return to full weight bearing confirmed by the operating surgeon

Power Analysis and Statistics

Retrospective review of ankle hardware removal cases indicates that 6% (8/126) of patients have their hardware removed for non-pain issues (e.g., infection, etc.) at 6 months and 17% (22/126) of patients have their hardware removed for pain on the medial or lateral side of the ankle at 6 months.⁸ Hence, the overall rate of hardware removal is 24% but if we can reduce half of the medial hardware removals the overall rate would be 14.5%. To detect this 9.5% difference, it would take 424 randomized patients (alpha = 0.05, and 80% power). Medial hardware removal will be prohibited for lateral hardware pain.

Utilizing the STRIDE database available at Stanford University, there have been 155 procedures involving fixation of the medial malleolus (CPT: 27766, 27814, 27822, 27823) over the past three years. Assuming a similar procedure burden at the other major Level I Trauma center and extrapolating this three-year data, we estimate the capability to enroll 500 patients over three years.

All continuous variables will be reported as the mean and errors are reported as standard deviation. All categorical variables will be reported as the subset number and percentage of the total. Comparisons will be performed with the appropriate statistical test when indicated. Statistical significance will be set at p less than 0.05 with an appropriate Bonferroni correction for multiple comparisons when indicated.

Budget

The vast majority of the budget will go toward an experienced fulltime clinical research coordinator, level II (CRCII, Table 2). This person is critical to our success. Appropriately, some funds will be devoted to insuring the proper training and certification for the CRCII involved in this project as well as supply adequate computing power and meet secure data storage needs. Some funds would be used by the principal investigator and co-investigators to offset local travel and travel to national and international meetings to present the findings of this interdisciplinary work, including the American Academy of Orthopaedic Surgeons (AAOS), the Orthopaedic Trauma Association (OTA), and the American Orthopaedic Foot and Ankle Society (AOFAS).

Table 2: General Budget

Expense			Effort	Cost
Personnel	Principal Investigator	[name]	10%	\$36,000/year
	Co-Investigator	[name]	3%	\$10,000/year
	Co-Investigator	[name]	3%	\$10,000/year
	Co-Investigator	[name]	3%	\$10,000/year
	Co-Investigator	[name]	3%	\$10,000/year
	Co-Investigator	[name]	3%	\$10,000/year
	CRCII	TBD: Stanford	100%	\$90,000/year

	CRCII	TBD: 3 rd center	75%	\$68,000/year
	CRCII	TBD: Kaiser	75%	\$68,000/year
Equipment	Computers			\$3,000/year
	Secure Storage			\$1,000/year
Training				\$5,000/year
Travel	Society Meetings			\$5,000/year
	Between Sites			\$5,000/year
				\$275,000/year

Acumed Study Summary	
Company	Stanford University
Title	Prospective, multi-center, randomized, controlled study evaluating the union rate, rate of medial malleolus hardware removal and clinical outcomes after medial malleolus fracture fixation with Acutrak headless compression screws
Short Title	Acutrak Fixation of Medial Malleolus Fractures
Protocol Number	
Treatment Device	Acutrak headless compression screws
Control Device(s)	Mini-fragment Plating, Antiglides Plating, Headed Unicortical Screws, Headed Bicortical Screws, Tension Band Wiring
Intended Use	The Acutrak headless compression screws are intended to provide fixation and anatomically reduce fractures of the medial malleolus that occur via supination-external rotation, pronation-external rotation, or pronation-abduction resulting in an oblique fracture pattern as well as supination-adduction resulting in a vertical shear fracture pattern.
Study Purpose	The fixation provided by the Acutrak headless compression screws provide sufficient fixation to achieve union and a favorable clinical outcome in both horizontal and vertical medial malleolus fractures when compared to bicortical and unicortical screw fixation, tension band wiring, and mini-fragment or buttress plating. However, minimizing the amount of dissection required for implantation as well as lack of prominent hardware surfaces will reduce the incidence and severity of hardware related pain and correspondingly the necessity of hardware removal.
Study Objectives	
Primary:
 
 • A successful outcome would be a reduction in the rate or severity of hardware related pain localized to the medial malleolus reducing the incidence of hardware removal from the medial malleolus at one year after sustaining an ankle fracture.
	
Secondary:
 
 • Another successful outcome would be an equivalent radiographic and clinical union rate when compared to traditional fixation methods. • Another successful outcome would be an equivalent PROMIS scores when compared to traditional fixation methods.
	
Safety Objective:
 
 • Prospectively establish equivalence with respect to fracture union rate after Acutrak headless compression screw fixation when compared to other fixation methods for medial malleolus fractures. • Prospectively establish equivalence with respect to Patient Reported Outcome Measurement Information System (PROMIS) scores after Acutrak headless compression screw fixation when compared to other fixation methods for medial malleolus fractures. • Prospectively establish superiority with respect to hardware related pain after Acutrak headless compression screw fixation when compared to other fixation methods for medial malleolus fractures. • Prospectively establish superiority with respect to the hardware removal rate after Acutrak headless compression screw fixation when compared to other fixation methods for medial malleolus fractures.

Evaluation Tools	Subjective: VAS Pain Score, Fracture Union Objective: Complications, PROMIS Scores
Subject Population	Patients sustaining a horizontal or vertical medial malleolus fracture as a result of supination-external rotation, pronation-external rotation, pronation-abduction, or supination-adduction of the ankle resulting in a fracture.
Critical Eligibility Criteria	Inclusion: All ankle fractures that undergo open reduction internal fixation of the medial malleolus in adults at or over 18 years-of-age will be considered for inclusion. Exclusion: 
 • pediatric ankle fractures • tibial plafond (pilon) fractures in children and adults • medial malleolar osteotomies to access the talus, perform an ankle fusion, or deal with a pathologic lesion, osteonecrosis, or infection • prior surgical treatment of the ankle for fracture, deformity, infection, neoplasia, or other pathologic process • non-weight bearing on one or both lower extremities prior to sustaining their ankle injury
Definition of Enrollment	Meeting Inclusion/Exclusion Criteria and Signed Informed Consent
Number of Subjects	Utilizing the STRIDE database available at Stanford University, there have been 155 procedures involving fixation of the medial malleolus (CPT: 27766, 27814, 27822, 27823) over the past three years. Assuming a similar procedure burden at another major Level I Trauma center at Kaiser Permanente Hospital, South Sacramento and extrapolating this three-year data, we estimate the capability to enroll and randomize over 500 patients requiring medial malleolus fixation over three years between the three centers.
Number of Sites	Three Level I Trauma Centers will participate: 
 • Stanford Hospital and Clinics • Kaiser Permanente – South Sacramento • Brigham and Women's Hospital- Boston
Procedure Schedule	See Table 1
Subject Duration	The estimated duration for each subject is 2 years. Subjects are released from postoperative follow-up after post-operative observation for two years.
Study Duration	The estimated duration of the study is 5 years: 3 years for enrollment and 2 year for postoperative follow-up for each enrolled subject.
Safety	All adverse events and complications will be continuously monitored throughout the study. The type and frequency will be analyzed by a medical monitor.
Statistical Methods	All continuous variables will be reported as the mean and errors are reported as standard deviation. All categorical variables will be reported as the subset number and percentage of the total. Comparisons will be performed with the appropriate statistical test when indicated. Statistical significance will be set at p less than 0.05 with an appropriate Bonferroni correction for multiple comparisons when indicated.

References

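### Aims 1 and 2 are to establish equivalence of union and PROMIS, but no margin, confidence-interval rule or analysis visit is set for either

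*Combined protocol and SAP*

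**What the plan says.** **The claim.** Specific Aims, Aim 1: "Prospectively establish equivalence with respect to fracture union rate after Acutrak headless compression screw fixation when compared to other fixation methods". Aim 2: "Prospectively establish equivalence with respect Patient Reported Outcome Measurement Information System (PROMIS) scores after Acutrak headless compression screw fixation". The study summary lists both as secondary objectives, for union in these words: "Another successful outcome would be an equivalent radiographic and clinical union rate when compared to traditional fixation methods". It repeats all four aims under Safety Objective.

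**The rule.** Power Analysis and Statistics, repeated under Statistical Methods in the summary, leaves the choice of test open and adds: "Statistical significance will be set at p less than 0.05 with an appropriate Bonferroni correction for multiple comparisons when indicated". The one sample-size calculation gives 424 patients to detect 24% against 14.5% hardware removal.

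**The timing.** The Follow-up Protocol and Table 1 schedule films up to 3 months and PROMIS at every contact to 2 years. The one-year time point in the objectives belongs to the primary objective on medial pain and hardware removal.

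**The endpoint.** Documentation of Fracture Union: "Union will be defined as a pain free fracture site on examination with evidence of radiographic healing", together with a return to full weight bearing. The Follow-up Protocol says: "Patients will be followed by telephonically once the fracture union is confirmed radiologically by the operating surgeon".

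**The concern.** Equivalence is a claim that the true difference is smaller than some stated amount. Without that amount there is nothing to test against. The open wording on tests does not exclude an equivalence test, but such a test cannot be run until a margin exists, and a margin chosen after the data are seen is open to bias. A p-value above 0.05 from a difference test shows only that a difference was not detected. Two of the four aims therefore have no defined route to their conclusion.

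A smaller issue concerns what is being compared. The formal definition of union includes a pain-free fracture site, while the Hypothesis predicts that "lack of prominent hardware surfaces will reduce the incidence and severity of hardware related pain". If some surgeons counted hardware pain as fracture-site pain, a component expected to differ by arm would enter the union comparison. It could hide a healing deficit with Acutrak or make equal healing look unequal.

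**Working it through.** **1. The plan's own figure.** Inputs from Power Analysis and Statistics: 24% against 14.5%, alpha 0.05, 80% power. The pooled proportion is (0.24 + 0.145)/2 = 0.1925.

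n per arm = [1.6449·√(2·0.1925·0.8075) + 0.8416·√(0.24·0.76 + 0.145·0.855)]² / 0.095² = 211.9, so 212 per arm and 424 in total.

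The figure is reproduced, with a one-sided 0.05 test; a two-sided test gives 540. The plan does not state sidedness, so both are shown in step 2. The calculation concerns hardware removal only.

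**2. How often a difference test would miss a union deficit.** Assumed: 1:1 allocation (212 per arm), the union rates shown and no dropout. With deficit d = 0.05, SE₀ the pooled standard error and SE₁ the unpooled one, the chance of a non-significant result is about Φ[(z·SE₀ − d)/SE₁].

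| Union, control vs Acutrak | SE₀ | SE₁ | Two-sided (z = 1.96) | One-sided (z = 1.6449) |
|---|---|---|---|---|
| 95% vs 90% | 0.0256 | 0.0255 | Φ(0.01) = 50% | Φ(−0.31) = 38% |
| 97% vs 92% | 0.0221 | 0.0220 | Φ(−0.30) = 38% | Φ(−0.62) = 27% |

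With an assumed 15% attrition (180 per arm), the two-sided figures become 56% and 45%.

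**3. What margin 212 per arm could support.** With no true difference and 80% power, margin = (z_CI + 1.2816)·SE, where z_CI is 1.96 for a 95% interval and 1.6449 for a 90% interval. For union, SE = √(2p(1−p)/212). For PROMIS with an assumed SD of 10, SE = 10·√(2/212) = 0.971.

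| Outcome (assumed) | SE | 95% CI | 90% CI |
|---|---|---|---|
| Union 95% | 0.0212 | 6.9 points | 6.2 points |
| Union 90% | 0.0291 | 9.4 points | 8.5 points |
| PROMIS, SD 10 | 0.971 | 3.1 points | 2.8 points |

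**4. Why the missing margin matters for feasibility.** Power = 2Φ(margin/SE − 1.6449) − 1 for a 90% interval. At 90% union, a 5-point margin gives margin/SE = 1.716 and power of 6%; a 10-point margin gives 3.432 and 93%. At 95% union the figures are 53% and over 99%. The same trial is hopeless or comfortable depending on a number the plan does not give.

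**5. The union texts side by side.** Documentation of Fracture Union is the only formal definition and has three parts: a pain-free site, radiographic healing and full weight bearing. The summary's radiographic and clinical union can be read as shorthand for it. The Follow-up Protocol mentions radiological confirmation only, in a sentence about moving patients to telephone contact. The clear mismatch is between that sentence and the definition. Table 1 has no film after 3 months and later contacts are by telephone and mail, so the three-part definition cannot be assessed as scheduled beyond 3 months.

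**The case against.** The appropriate test for an equivalence aim is an equivalence test, so the general wording could cover one. That is true, but it supplies neither margin nor visit. Both aims are secondary in the summary, which limits the severity without removing the gap. It is also fair that intervals reported at the end could be judged against an externally justified margin. Prespecification is stronger, but its absence does not make the data worthless.

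Three stronger readings are tempting and are not supported:

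- **That the sponsor will treat non-significance as equivalence.** The documents do not say so. The miss rates in step 2 show why it should be ruled out; they do not describe a stated plan.
- **That union has three conflicting definitions.** There is one definition, one phrase compatible with it, and one logistics sentence that differs.
- **That hardware pain biases the union comparison.** The definition refers to the fracture site, and the removal criteria keep sensitivity apart from non-union: "All bothersome sensation will be subjected to hardware removal and noted as removal for sensitivity". Surgeons are evidently expected to tell the two apart. What remains is that the definition does not say hardware pain is excluded. Any numerical effect depends on the margin chosen. With equal 95% healing, 212 per arm, a 95% interval and controls scored 2 or 3 points lower, power falls from 82% to 56% or 37% at a 7-point margin, but only from 99% to 93% or 83% at a 10-point margin.

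**Conclusion.** The point holds. Equivalence is claimed for union and PROMIS with no margin, interval rule or named analysis visit, and the general rule of p below 0.05 from a difference test cannot deliver it. Under the assumed rates and 1:1 split, such a test would pass over a true 5-point union deficit in 38% to 50% of trials two-sided, or 27% to 38% one-sided. The absence of the rule is a fact of the text; the sizes rest on union rates and a PROMIS SD that the documents do not give. It does not follow that 424 patients are too few for equivalence, since that depends on the missing margin. The mismatch over union is a secondary matter of wording, and any bias through hardware pain is possible, not shown. This should be corrected, but as a matter of secondary objectives it does not threaten the primary one.

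**What to change.** **Main change, before data review:**

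- State a justified margin and one analysis visit for union, and the same for PROMIS.
- Claim equivalence only if the whole confidence interval for Acutrak minus control lies within the margin. State the level: 95%, or 90% for two one-sided tests at 0.05.
- State that p ≥ 0.05 is not evidence of equivalence.

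**Secondary change:**

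- Reconcile the Follow-up Protocol sentence with Documentation of Fracture Union. Keep the latter as the definition unless the sponsor chooses otherwise.
- State whether hardware pain counts against a pain-free fracture site.
- Report the radiographic component separately by arm, from the films already in Table 1.

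**Cost.** Wording and a little more analysis. No visits or films are added if 3 months is the union visit, although the sponsor should justify that time, since no section says union is expected by then. A later visit would need films that are not scheduled. The real price is commitment: the sponsor must fix margins and may then be unable to claim equivalence. The table in step 3 of the working shows roughly what 212 per arm can support, but a margin needs a clinical justification and should not be set by what the sample size allows.

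### Aims 1 and 2 name equivalence for union and PROMIS where the hypothesis needs only that Acutrak is not worse; one-sided non-inferiority, with margins set in advance, would fit better

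*Combined protocol and SAP*

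**What the plan says.** The Specific Aims sort the four comparisons into two kinds. Aim 1 is to "Prospectively establish equivalence with respect to fracture union rate after Acutrak headless compression screw fixation" and Aim 2 is to "Prospectively establish equivalence with respect Patient Reported Outcome Measurement Information System (PROMIS) scores after Acutrak headless compression screw fixation". Aim 3, by contrast, is to "Prospectively establish superiority with respect to hardware related pain after Acutrak headless compression screw fixation", and Aim 4 asks for superiority on hardware removal.

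The Acumed Study Summary repeats this. Under Study Objectives, Secondary: "Another successful outcome would be an equivalent radiographic and clinical union rate when compared to traditional fixation methods" and "Another successful outcome would be an equivalent PROMIS scores when compared to traditional fixation methods". Its Safety Objective entry lists all four aims again, with the words equivalence and superiority underlined.

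The Hypothesis points one way. It says that the screws "provide sufficient fixation to achieve union and a favorable clinical outcome in both horizontal and vertical medial malleolus fractures" and that the lower dissection and lack of prominent hardware "will reduce the incidence and severity of hardware related pain and correspondingly the necessity of hardware removal".

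Pain also enters the union endpoint. Under Documentation of Fracture Union: "Union will be defined as a pain free fracture site on examination with evidence of radiographic healing", together with full weight bearing.

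The plan gives no margin, confidence-interval rule or named test for Aims 1 and 2, and these aims name no PROMIS domain or time point. Power Analysis and Statistics leaves the choice to whatever test is appropriate, and its only sample size, 424, is for hardware removal.

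**The concern.** Equivalence in its usual statistical meaning requires the difference to lie within a margin on both sides. A result that is too good fails it, just as one that is too poor does. Nothing in the rationale calls for ruling out a better result with Acutrak; the clinical question is whether less prominent hardware is bought at the price of worse healing or function.

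The aims may also pull against each other. If Acutrak reduces pain, as Aim 3 expects, more patients may meet a union definition that requires a pain-free site, and PROMIS scores may plausibly improve. Both would move Aims 1 and 2 away from zero in the favourable direction.

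Two things are at stake. A favourable result on union or PROMIS could have to be described as equivalence not shown. And the upper bound costs power on the aims that the summary lists as safety objectives, even when the arms do not differ.

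**Working it through.** **The plan's own figure.** With removal rates of 24% and 14.5% (mean 0.1925), the pooled-variance formula for two proportions at 80% power is

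n per arm = [z(1−α)·√(2·0.1925·0.8075) + 0.842·√(0.24·0.76 + 0.145·0.855)]² / 0.095².

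With z = 1.645 (one-sided 0.05) this gives 211.9, so 212 per arm and 424 in total, as stated. A two-sided test would need 270 per arm, 540 in total. The figure belongs to Aim 4. It is used here only to fix 212 per arm, assuming 1:1 allocation and no losses.

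**Assumed inputs.** The plan gives no PROMIS SD, union rate or margin. I take PROMIS SD 10 with margins of 2, 3 and 5 points, union of 95% in the control arm with margins of 5 and 10 points, and one-sided tests at 0.05.

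**Formulas** (normal approximation; d = true benefit of Acutrak, m = margin, Φ = standard normal distribution function):

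- Equivalence by two one-sided tests: Φ((m−d)/SE − 1.645) − Φ(−(m+d)/SE + 1.645)
- Non-inferiority: Φ((m+d)/SE − 1.645)
- SE for PROMIS: 10·√(2/212) = 0.971
- SE for union: √(p₁q₁/212 + p₂q₂/212)

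**No true difference.**

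- PROMIS, m = 3: m/SE = 3.089. Non-inferiority is Φ(1.444) = 93%. Equivalence is Φ(1.444) − Φ(−1.444) = 85%.
- Union 95% in both arms, m = 5 points: SE = 0.0212 and m/SE = 2.362. Non-inferiority is Φ(0.717) = 76%. Equivalence is Φ(0.717) − Φ(−0.717) = 53%.

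**True benefit for Acutrak.**

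| Endpoint | True benefit | Margin | Equivalence shown | Non-inferiority shown |
|---|---|---|---|---|
| PROMIS | 2 points | 2 | 4% | 99% |
| PROMIS | 2 points | 3 | 27% | >99% |
| PROMIS | 2 points | 5 | 93% | >99% |
| PROMIS | 3 points | 3 | 5% | >99% |
| Union | 97% vs 95% | 5 points | 45% | 98% |
| Union | 97% vs 95% | 10 points | 99% | >99% |
| Union | 99% vs 95% | 10 points | 98% | >99% |

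**At the stricter one-sided 0.025 level** the pattern is the same. For PROMIS with a margin of 0.3 SD and no true difference, power at 212 per arm is 74% for equivalence and 87% for non-inferiority. For 80% power, equivalence needs 234 per arm and non-inferiority 175. For union at 90% in both arms with a 10-point margin, the numbers are 190 and 142.

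**The case against.** The strongest reply is that the plan defines no two-sided test at all. There is no margin, no interval rule and no statement that a better result counts as failure. The summary calls equivalent results another successful outcome, which does not make a better result unsuccessful, and equivalence may be loose wording for no loss. This stands in part. The deliberate contrast with superiority, underlined in the summary, makes the ordinary meaning the natural reading, but the documents do not settle it.

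A reader might infer that a real benefit on union or PROMIS would make the trial miss its own aims, whatever margin is chosen. The documents do not support that. An upper bound exists at any margin, but its consequence depends on the margin: a 2-point PROMIS benefit passes 93% of the time at a margin of 5, and the union benefits tabulated above pass 98–99% of the time at 10 points. The ceiling at 100% also limits how far union can improve.

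A shift of 2 to 3 PROMIS points is not established either. The plan's own effect is 9.5 percentage points fewer removals. If only patients spared a removal gained, and each gained 5 to 10 points (an assumption), the mean would move by 0.095 × 5 = 0.475 to 0.095 × 10 = 0.95 points. Equivalence at margin 3 would then be shown about 80% to 67% of the time. Less pain in patients who keep their hardware could add to this, but no figure in the plan says how much.

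Finally, the missing margin and test are the more basic gap. That is right, and a change of word alone would not close it. But supplying a margin while keeping equivalence would leave the unneeded upper bound and its cost in power.

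**Conclusion.** The point holds as a mismatch between the stated target and the trial's question. Equivalence on union and PROMIS asks for an upper bound that the hypothesis does not need. It could count against Acutrak when the benefit is near or above the margin, and it loses power even with no true difference: 8 percentage points for PROMIS (93% to 85%) and 23 for union (76% to 53%) under the assumptions above. At wide margins the loss is negligible; for union at 95% with a 10-point margin, both tests have power above 99%.

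Every one of these figures rests on an assumed SD, union rate, margin and test level. A miss caused by a real benefit is possible, not certain.

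The affected aims are secondary and safety objectives. The primary objective, on medial hardware pain and removal, is a superiority claim and is untouched, so this is a worthwhile low-cost improvement and not a condition for the trial to proceed.

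**What to change.** In the Specific Aims (Aims 1 and 2), and in the Secondary and Safety Objective entries of the Acumed Study Summary, replace equivalence with one-sided non-inferiority. For each endpoint, state the margin with its justification, the test level and the time point, all before data are seen; a change made after a favourable result would look post hoc.

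Decision rule: conclude non-inferiority when the confidence bound on the unfavourable side lies within the margin. For union, the lower bound for Acutrak minus control must lie above minus the margin. For PROMIS, name the domain, so that the unfavourable direction is clear. Allow a superiority statement if the two-sided interval also excludes zero.

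If two-sided equivalence is really intended, keep the word, give the margins and say why a better result with Acutrak needs to be ruled out.

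Cost: wording in three places, plus the work of choosing and defending two margins, which either version of the aims needs. The trial gives up the claim that Acutrak is not better than traditional fixation on these endpoints.
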